10.4.2. Continuous Glucose Monitoring

Supplemental information on glucose level trends will be collected using a CGM device. If subjects do not already have a study-issued CGM device (as these are provided in Study 401GSDIA01), a study-issued CGM will be provided. Subjects should bring their CGM device to each visit, containing CGM data from the 28 days prior to the visit (Table 1). If a study visit is conducted remotely (home healthcare visit or telemedicine), or if a study visit is skipped entirely for any reason, arrangements will be made for the subject to ship the CGM receiver (ideally, containing CGM data from the 28 days prior to the remote/missed visit) to the clinical site.

Data from the subject's CGM device will be transferred to the Sponsor throughout the study, including a final data transfer at the end of the Week 312 visit or early withdrawal. It is recommended that all CGM sensors should be paired with the study-issued receiver, regardless of whether the subject is also pairing the sensor with their own personal device (i.e. smartphone). The receivers should be maintained in bluetooth range of the sensors, whenever possible, and the data from the receivers should be uploaded on the study-issued laptop on a weekly basis. Additional details regarding the care and use of the CGM device and sensors and data transfer to the Sponsor are provided in the Manual of Operations.

10.4.3. Morning Glucose Assessments

If a subject is unable to use the assigned CGM, the subject should collect morning glucose levels at least 2 mornings per week throughout the study (Table 1). Subjects should adhere to their prescribed overnight cornstarch diet. Morning glucose levels should be measured using the subject's own glucose monitoring device before taking their morning dose of cornstarch. The collection time, glucose level, and prior day's overnight cornstarch use should be collected on the Morning Glucose Level monitoring worksheet provided by the site. Subjects should bring the completed worksheets to each study visit. Data collected on the worksheet will be captured on the appropriate page of the eCRF.

10.4.4. Magnetic Resonance Imaging

An MRI of the liver will be conducted at the time points specified in the Schedule of Events (Table 1). The MRI should be completed after the controlled fasting challenge to avoid having to replace the CGM sensor prior to the fasting challenge. Magnetic resonance imaging will be conducted at the study site; however, all results will be transmitted to a central radiologist for interpretation to ensure consistent assessment across study sites. Instructions for transmitting MRI results will be provided separately. Magnetic resonance imaging results will be analyzed for hepatic fat fraction, liver volume, and the relative change in each from Study 401GSDIA01 Baseline (Day 0).

Completion of the MRI will be recorded on the appropriate page of the eCRF. At the end of the study, images may be stored for up to 15 years and analyzed to better understand the effect of DTX401 on GSDIa or other metabolic deficiencies. The choice to allow retention and future analysis will be optional.

10.4.5. Liver Ultrasound

An ultrasound of the liver will be conducted at the time points specified in the Schedule of Events (Table 1). The ultrasound should be completed prior to the controlled fasting glucose challenge. The liver ultrasound will be conducted at the study site and analyzed for liver volume.

10.5. Biomarker Assessments

Not applicable.

10.6. Patient-Reported and Clinician-Reported Outcomes

10.6.1. Health-Related Quality of Life and Sleep Quality Assessments

Subjects will be asked to complete the following HRQoL and sleep quality assessments (Table 1).

- Patient-Reported Outcomes Measurement Information System (PROMIS®)-29 (Appendix 1)
- PROMIS Social Isolation (Appendix 2)
- Pittsburgh Sleep Quality Index (Appendix 3)
- Patient Global Impression of Severity (Appendix 4)
- Patient Global Impression of Change (Appendix 5)

Subjects will complete the HRQoL and sleep quality assessments prior to invasive assessments being conducted. Subjects may pause to rest during administration of the HRQoL and sleep quality assessments, but the entire set of assessments should be completed in 1 session. Study staff should review the completed forms for completeness once the subject returns the forms to staff.

Data collected on the HRQoL and sleep quality assessments will be captured on the appropriate page of the eCRF.

10.6.2. Endpoint Outcomes Interview (Year 2 – Exit Interview)

A 30-minute scripted telephone interview will be conducted at Week 104 (or at Early Withdrawal, if the subject withdraws prior to Week 104) to better quantify the subject experience in the study. The interview will be conducted by a third-party vendor, Endpoint Outcomes, specializing in the capture of caregiver and subject-reported data. Endpoint Outcome uses a script as an interview guide to serve as a basis for the discussion. The interview will be conducted by phone.

The subject has consented to the interview per the study's main ICF. However, prior to the start of the interview, Endpoint Outcomes will verbally ask for the subject's consent for the interview to be audio-recorded. With the subject's verbal consent, the interview will be audio-recorded, and the interviewer will proceed through a script. If the subject does not give permission for the session to be audio-recorded, the interview will not proceed. Subjects will be asked about their experience in the study. They may refuse to answer any question in the interview and may stop at any time.

Site staff will facilitate the phone call so that the subject's contact information remains anonymous. Personal information (including subject's name and telephone number) will remain anonymous and will not be provided to the Sponsor or Endpoint Outcomes. Subjects will be identified only by their study specific subject IDs.

All digital recordings will be stored by Endpoint Outcomes in a secure place where only Endpoints Outcome personnel directly related to this study will be able to access it. The audio interviews will be transcribed by a transcription company under contract and a confidentiality agreement, who will provide the written transcripts that will be further analyzed by Endpoint Outcomes. The transcription company is also contracted to ensure that transcripts will not contain any personal identifying information (eg, reference of first names) that may have been revealed during the interview process; personal identifying information will be removed and will not appear in the final transcript. Data from the interview will be shared with the Sponsor only after all identifying information has been removed.

10.7. Pharmacokinetic Assessments

Not applicable.

10.8. Other Assessments

10.8.1. Demographic and Medical History Assessments

As allowed by local laws and regulations, the following demographic data may be captured on the appropriate page in the eCRF: date of birth, sex, race, and ethnicity.

Medical history will be assessed at Visit 1 (Table 1). Any AEs that are ongoing at the completion of Study 401GSDIA01 will be considered medical history in Study 401GSDIA02.

10.8.2. Assessment of Prescribed Diet and Dietary Intake

The subject's prescribed diet will be reviewed at each study visit, and if possible, on a monthly basis through the final study visit (Table 1). Content, quantity, and frequency of diet intake (including daily carbohydrate intake) will be recorded on the appropriate page of the eCRF.

10.8.3. Assessment of Cornstarch (or Equivalent) Use

The subject's average daily use of cornstarch (or equivalent) will be reviewed at each study visit, and if possible, on a monthly basis through the final study visit (Table 1). Follow-up phone calls may occur regularly (approximately once a month) to further discuss if adjustments are needed for a subject's cornstarch use. Quantity and frequency of intake will be recorded on the appropriate page of the eCRF.

10.9. Appropriateness of Measurements

All measurements will be performed using standard methods that are generally recognized as reliable, accurate, and relevant.

11. SAFETY DATA COLLECTION, RECORDING, AND REPORTING

11.1. Reporting and Follow-up of Adverse Events

11.1.1. Adverse Event Terminology

An **AE** is defined as any untoward medical occurrence associated with the use of a drug in humans, whether or not considered drug related. An AE can therefore be any unfavorable and unintended sign (including an abnormal laboratory finding, for example), symptom, or disease temporally associated with the use of a medicinal (investigational) product, whether or not related to the medicinal (investigational) products.

An **SAE** is an AE that at any dose, in the view of either the Investigator or Sponsor, results in any of the following serious outcomes:

- Death
- A life-threatening AE
- *A life-threatening AE is an event that, in the view of either the Investigator or Sponsor, places the patient or subject at immediate risk of death. It does not include an AE or suspected adverse reaction that, had it occurred in a more severe form, might have caused death.*
- Inpatient hospitalization or prolongation of existing hospitalization
- *Note that hospitalizations planned prior to study enrollment (eg, for elective surgeries) are not considered SAEs; however, an event that prolongs this type of hospitalization would be considered an SAE. Hospitalizations that occur for pre-existing conditions that are scheduled after study enrollment are considered SAEs.*
- Persistent or significant incapacity or substantial disruption of the ability to conduct normal life functions
- A congenital anomaly/birth defect
- Important medical events that may not result in death, be immediately life-threatening, or require hospitalization may be considered serious when, based upon appropriate medical judgment, they may jeopardize the patient or subject and may require medical or surgical intervention to prevent one of the outcomes listed in the definition. Examples of such medical events include allergic bronchospasm requiring intensive treatment in an emergency room or at home, blood dyscrasias or convulsions that do not result in inpatient hospitalization, or the development of drug dependency or drug abuse

Nonemergent hospitalization for cornstarch management will not be considered an SAE.

A **suspected adverse reaction** is any AE for which there is a reasonable possibility that the drug caused the AE. For the purposes of expedited safety reporting, “reasonable possibility” means there is evidence to suggest a causal relationship between the drug and the AE. Suspected

adverse reaction implies a lesser degree of certainty about causality than adverse reaction, which means any AE caused by a drug.

As there is limited prior clinical experience with DTX401, reference safety information for assessing whether an AE is a suspected unexpected serious adverse reaction (SUSAR) is currently not available. Therefore, any SAE considered related to DTX401 will be considered a **SUSAR** and reported immediately. The SAE should be treated with appropriate supportive and medical care deemed necessary for the well-being of the subject.

11.1.2. Severity of Adverse Events

The severity/toxicity, or intensity, of an AE refers to the extent to which an AE affects the subject's daily activities. The Investigator should rate the intensity of an AE as Grade 1, 2, 3, 4, or 5 based on their medical judgment. The most current version of the National Cancer Institute Common Terminology Criteria for Adverse Events (NCI, 2018) can be used to guide the rating of an AE.

In the event that an AE occurs during the study that is not captured by the CTCAE, the AE should be graded according to the general guidelines outlined in [Table 3](#).

Table 3: General Guidelines for Grading Events Not Captured by the CTCAE

| Grade | Criteria |
|---------|-------------------------------------------------------------------------------------------------------------------------------------------------------------------------------------|
| Grade 1 | Mild; asymptomatic or mild symptoms; clinical or diagnostic observations only; intervention not indicated. |
| Grade 2 | Moderate; minimal, local, or noninvasive intervention indicated; limiting age-appropriate instrumental ADL. ¹ |
| Grade 3 | Severe or medically significant but not immediately life threatening; hospitalization or prolongation of hospitalization indicated; disabling; limiting self-care ADL. ² |
| Grade 4 | Life-threatening consequences; urgent intervention indicated. |
| Grade 5 | Death related to AE. |

Abbreviations: ADL = activities of daily living; AE = adverse event; CTCAE = Common Terminology Criteria for Adverse Events.

¹ Instrumental ADL refers to preparing meals, shopping for groceries or clothes, using the telephone, managing money, etc.

² Self-care ADL refers to bathing, dressing and undressing, feeding self, using the toilet, taking medications, and not bedridden.

Changes in the severity/toxicity of an AE should be documented to allow an assessment of the duration of the event at each level of intensity to be performed. Adverse events characterized as intermittent do not require documentation of onset and duration of each episode.

Terminology Clarification: The term “severe” is often used to describe the intensity (severity) of a specific event (as in mild, moderate, or severe myocardial infarction); the event itself, however, may be of relatively minor medical significance (such as severe headache). The severity is not the same as “serious” which is based on subject/event outcome or action criteria and is usually associated with events that pose a threat to a subject's life or functioning (Section 11.1.1). Seriousness (not severity) serves as a guide for defining regulatory reporting obligations (Section 11.1.4.2).

11.1.3. Relationship of Adverse Events to Investigational Product

The Investigator will assess the potential relationship of the AE to IP using the following descriptions.

Categories of attributions for “unrelated” events:

- **Unrelated:** This category applies to an AE that *is clearly not related* to the investigational agent/procedure.

Categories of attributions for “related” events:

- **Possibly Related:** This category applies to an AE that *may be related* to the investigational agent/procedure.
- **Probably Related:** This category applies to an AE that *is likely related* to the investigational agent/procedure.
- **Definitely Related:** This category applies to an AE that *is clearly related* to the investigational agent/procedure.

For the purposes of reporting to regulatory agencies, AEs deemed as definitely, probably or possibly related will be considered related.

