Abbreviations: AAV8 = adeno-associated virus serotype 8; AE = adverse event; EOS = end of study; EW = early withdrawal; G6Pase = glucose-6-phosphatase; HRQoL = health-related quality of life; IgG = immunoglobulin G; MRI = magnetic resonance imaging; SAE = serious adverse event.

Note: Specified visits that include a controlled fasting challenge will require an approximate 24-hour inpatient stay (Visit 1, Weeks 78, 104, 156, 208, 260, and EW visit, as applicable). All other visits (Weeks 65, 91, 130, 182, 234, 286, and 312) will be conducted on an outpatient basis (approximately 1.5 to 2 hours).

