12.1.1. Primary Endpoint

The primary endpoint of this study is as follows:

- The incidence of AEs and SAEs for each cohort and overall assessed by severity and relationship to IP

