6.9.1. Adverse Events

Adverse events will be coded by system organ class (SOC) and preferred term (PT) using the current version of Medical Dictionary for Regulatory Activities.

An AE (classified by preferred term) will be considered a treatment emergent adverse event (TEAE) if it occurred on or after the first dose of IP.

AEs from both studies 401GSDIA01 and 401GSDIA02 will be combined for this analysis. Further, AEs from Study 401GSDIA02 will also be summarized separately.

Subject incidence of TEAEs will be tabulated as the follows. The number of events will also be included.:

- Summary of TEAEs
- TEAEs by SOC and PT
- Related TEAEs by SOC and PT

- Serious Related TEAEs by SOC and PT
- Grade 3 or 4 TEAEs by SOC and PT
- Fatal TEAEs by SOC and PT
- TEAEs leading to discontinuation of study by SOC and PT
- TEAEs by PT
- TEAEs by PT and greatest severity
- TEAEs by their time of occurrence (<1, 1-2, 2-3, 3-4, 4-5, 5-6 years since the IP administration)

The severity will be based on the most current version of CTCAE. If an AE cannot be graded based on CTCAE, the investigator will assign a severity based on 1 = mild, 2 = moderate, 3 = severe, 4 = life threatening, and 5 = death. Detailed listings for all AEs, serious TEAEs, TEAEs leading to the discontinuation of study, and death will also be generated.

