6.9.1.2. Potential Risks and Adverse Events of Special Interest

Adrenal insufficiency is considered a potential risk of study-related procedures associated with use of corticosteroids and is an AESI. Since subjects are enrolled in Study 401GSDIA02 at 52 weeks after IP infusion in Study 401GSDIA01, it is not expected that corticosteroids will be administered in 401GSDIA02 study to minimize or prevent potential vector-induced hepatic events (eg, transaminase elevations). However, in the event elevated ALT or AST is observed in 401GSDIA02 study due to the AAV8 vector and corticosteroids are required (and is not due to underlying disease), subject incidence of TEAEs of adrenal insufficiency will be tabulated by SOC and PT. MedDRA search strategy to identify PTs for these events is included in [Appendix 2](#).

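### Protocol 11.1.3 asks for relationship to IP but defines every category by agent or procedure, so an AE caused by a fasting challenge can enter the primary endpoint as IP-related

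*Protocol*

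**What the plan says.** Protocol 11.1.3 is headed as relationship to Investigational Product and opens accordingly: "The Investigator will assess the potential relationship of the AE to IP using the following descriptions". The four descriptions then use a different object. For possibly related, the text is "This category applies to an AE that *may be related* to the investigational agent/procedure". The probable and definite categories name the same pair, and the unrelated category is reserved for events with clearly no link to it. For regulatory reporting, "AEs deemed as definitely, probably or possibly related will be considered related".

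Protocol 11.1.4.1 lists relationship to IP among the details every AE record must contain and lists no relationship to study procedures. The primary endpoint in Protocol 12.1.1 rests on that item: "The incidence of AEs and SAEs for each cohort and overall assessed by severity and relationship to IP". SAP 6.9.1 tabulates "Related TEAEs by SOC and PT" and a serious related counterpart. It plans no table of procedure-related events.

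Elsewhere the object is the product alone. Protocol 11.1.1 says "Therefore, any SAE considered related to DTX401 will be considered a" SUSAR, and SAP Appendix 1 imputes a missing causal relationship to DTX401 as related. The SAP does separate procedure risk from product risk once, in 6.9.1.2: "Adrenal insufficiency is considered a potential risk of study-related procedures associated with use of corticosteroids".

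On exposure to procedures, the note to Figure 2 in Protocol 7.1 says "Specified visits that include a controlled fasting challenge will require an approximate 24-hour inpatient stay" and lists Visit 1, Weeks 78, 104, 156, 208 and 260, and early withdrawal where applicable.

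**The concern.** A site has one grade to give and two objects to grade against. If an investigator reads the category text literally, an AE caused by the fast or by the indwelling catheter cannot be called unrelated, because it is not clearly unlinked to the agent/procedure pair. It then appears as related in an endpoint defined by relationship to IP. Another investigator, following the lead-in sentence, would grade the same event unrelated. Two careful readers can differ, and nothing in the protocol or SAP settles which of them is right.

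What is at stake is how the related-event tables are read. The study follows subjects for years after a single dose given in the previous study. A challenge-caused event graded related in Year 4, for example, would look in those tables like a late effect of the vector.

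**Working it through.** No figure in the plan depends on this wording, so there is nothing to reproduce. The check compares the passages and then gives the scale.

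**1. Object of the causality judgement, place by place**

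| Place | Object |
|---|---|
| Protocol 11.1.3, heading and lead-in | IP |
| Protocol 11.1.3, four categories | agent/procedure |
| Protocol 11.1.4.1, required AE details | IP |
| Protocol 12.1.1, primary endpoint | IP |
| Protocol 11.1.1, SUSAR rule | DTX401 |
| SAP Appendix 1, imputation | DTX401 |
| SAP 6.9.1, related tables | not stated |

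The category definitions are the only entry that brings in procedure, and they are the text by which the grade is assigned.

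**2. What procedure can mean**

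- *Administration of the vector.* This is a natural reading in a gene-transfer protocol. However, no IP is given here (Protocol 9.1), and SAP 6.9.1.1 treats infusion-related reactions as not applicable to this study.
- *Any study procedure.* Protocol section 10 is the study procedures section and contains the fasting challenge (10.4.1). Table 1 has a procedure column, and the challenge is one of its rows.

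Both readings are open. The second fits the protocol's own usage.

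**3. Number of challenges** (schedule from Protocol 7.1.3.1; 12 subjects in cohorts of 3 from Protocol 5.4)

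- Through Week 260: 6 per subject; 6 × 12 = 72.
- If all subjects leave at Week 208: 5 × 12 = 60.
- Early-withdrawal and unscheduled challenges are extra.

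**4. Effect of one misattributed subject**, assuming that no subject in the group otherwise has a related TEAE (exact 95% Clopper-Pearson intervals)

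| Group | Incidence | 95% interval |
|---|---|---|
| One cohort | 1/3 = 33.3% | 0.8 to 90.6% |
| Cohorts 2 to 4 combined | 1/9 = 11.1% | 0.3 to 48.2% |
| Overall | 1/12 = 8.3% | 0.2 to 38.5% |

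For the any-related-TEAE count, the shift needs a subject with no other related TEAE. In the combined table that means none since dosing in Study 401GSDIA01. In a single SOC/PT row, it needs only no other related TEAE in that row.

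**5. Chance of at least one such event.** The documents give no rate of procedure-caused AEs. The rates p per challenge below are assumptions, with challenges taken as independent. The formula is 1 − (1 − p)^m, where m is the total number of challenges.

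| Assumed p | m = 60 | m = 72 |
|---|---|---|
| 0.5% | 26.0% | 30.3% |
| 1% | 45.3% | 51.5% |
| 2% | 70.2% | 76.7% |
| 5% | 95.4% | 97.5% |

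This is the chance that an event arises for which the wording matters. It is not the chance that the event is graded related.

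**The case against.** The strongest reply is that the instruction itself, the required AE record, the endpoint and the imputation rule all speak of IP or DTX401, so a sensible investigator would grade a pure catheter or fasting event as unrelated. That is a fair reading. It stands against any claim that such events are certain to be counted as DTX401-related, because no passage directs it. It does not remove the conflict, because the literal category text points the other way.

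Four further points limit the concern.

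- **SUSARs.** A reader might infer that challenge-caused SAEs become SUSARs. The rule requires relatedness to DTX401, so this happens only if an agent/procedure grade is carried across. The pooling sentence in 11.1.3 makes that possible, but nothing instructs it.
- **Expected hypoglycemia.** A challenge is designed to end at glucose below 54 mg/dL, at signs or symptoms, or at 15 hours (Protocol 10.4.1). Protocol 10.3.7 keeps clinically significant GSDIa-associated safety assessments out of AE reporting unless they are judged more severe than expected. The most obvious challenge outcome may therefore never be recorded as an AE. Catheter complications are not covered by that exception.
- **Steroids.** SAP 6.9.1.2 does not expect corticosteroids in this study, and adrenal insufficiency has its own search strategy. Steroid effects add little here.
- **The eCRF.** It is not among the documents, so a procedure item there cannot be ruled out.

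It can also be said that misgrading would inflate related counts, which is the cautious direction for safety. That is true, but it does not make the tables easier to interpret.

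**Conclusion.** The causality scale conflicts with its own heading, with its lead-in and with the primary endpoint, and nothing in the protocol or SAP corrects it. AEs caused by a fasting challenge or its catheter can be graded related and be reported as IP-related. One affected subject with no other related TEAE shifts incidence by 1/3 in a cohort and by 1/12 overall. How often this would occur is unknown, because the documents give no procedure AE rate.

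A reader might go further and infer that the study cannot answer its question about long-term safety. The documents do not support that. SAP 6.9.1 also plans all-causality TEAEs by SOC and PT, by greatest severity and by year since dosing, with detailed listings. The hepatic, nerve, malignancy and thrombotic microangiopathy tables use MedDRA searches that do not depend on attribution. What is lost is a clear meaning for the related and serious related tables. The defect is worth correcting, and its reach is confined to attribution.

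**What to change.** 1. In Protocol 11.1.3, word all four categories as relationship to DTX401, including its administration, and drop the undefined procedure.
2. Record relationship to study procedures (for example the fasting challenge, its catheter or imaging) as a separate yes/no item. If the eCRF already has one, cite it in the protocol and SAP.
3. In SAP 6.9.1, state that the related and serious related TEAE tables use the DTX401 attribution, and add a separate table of procedure-related TEAEs.
4. Keep the original grades for events already recorded. Re-querying only events already graded related, in an open-label study, could move counts in one direction only. Any later split should therefore appear solely as a supplementary listing beside the original grades.

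The cost is one eCRF item if none exists, short wording changes in the protocol and SAP, and one added table. The downside is that attribution before and after the change will not be fully uniform, which the report should say. No clinical procedure changes.
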